4. Whether it constitutes a SAE (see [Section 7.1.2](#) for definition of SAE) and which seriousness criteria have been met

5. Action taken regarding investigational treatment and other treatment (prednisolone). All AEs must be treated appropriately. Treatment may include one or more of the following:

- Dose not changed
- Dose Reduced/increased
- Drug interrupted/withdrawn.

6. Its outcome (not recovered/not resolved; recovered/resolved; recovering/resolving, recovered/resolved with sequelae; fatal; or unknown).

Conditions that were already present at the time of informed consent should be recorded in the patient's medical history.

Adverse events (including laboratory abnormalities that constitute AEs) should be described using a diagnosis whenever possible, rather than individual underlying signs and symptoms.

Adverse event monitoring should be continued for at least 20 weeks (or 5 half-lives or end of study visit, whichever is longer) following the last dose of study treatment.

Once an AE is detected, it must be followed until its resolution or until it is judged to be permanent(e.g. Continuing at the end of the study), and assessment should be made at each visit (or more frequently, if necessary) of any changes in severity, the suspected relationship to the investigational drug, the interventions required to treat it, and the outcome.

Information about common side effects already known about the investigational drug can be found in the IB. This information will be included in the patient informed consent and should be discussed with the patient during the study as needed. Any new information regarding the safety profile of the medicinal product that is identified between IB updates will be communicated as appropriate, for example, via an Investigator Notification or an Aggregate Safety Finding. New information might require an update to the informed consent and has then to be discussed with the patient.

Abnormal laboratory values or test results constitute AEs only if they fulfill at least one of the following criteria:

- they induce clinical signs or symptoms
- they are considered clinically significant
- they require therapy

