### **9.5.2 Safety variables**

For all safety analyses, the Safety Set will be used. All listings and tables will be presented by treatment group.

Safety summaries (tables, figures) include only data from the on-treatment period with the exception of Baseline data which will also be summarized where appropriate (e.g. change from Baseline summaries). In addition, a separate summary for death including on treatment and post treatment deaths will be provided. In particular, summary tables for AEs will summarize only on-treatment events, with a start date during the on-treatment period (treatment-emergent AEs).

Treatment-emergent AEs are defined as events which start after the first dose of study medication or events present prior to the first dose of study medication but increase in severity after dosing based on preferred term and within last dose + 20 weeks.

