2.8.1 Adverse events

Adverse events will be coded by primary SOC and PT according to the MedDRA version 23.0 or later and will be presented for the whole study period. Only treatment emergent AEs (TEAEs) will be summarized.

Treatment emergent AEs are defined as events started after the first dose of study treatment or events present prior to the first dose of study treatment but increased in severity after dosing based on preferred term and within last dose + 84 days. For handling of missing or incomplete start and end dates, refer to Section 5.1.2.

Treatment emergent AEs will be summarized for each treatment group by presenting the crude incidence of patients having any TEAE and having a TEAE by primary SOC and by PT. Patients who experienced multiple AEs for a PT will be counted once for that PT, similarly for patients with multiple AEs per primary SOC. For summaries of TEAEs by severity, if a patient reports more than one AE with the same PT, only the AE with the maximum severity will be counted. Similarly, if a patient reports more than one AE within the same primary SOC, the event with the maximum severity will be counted for the SOC level. If the severity of a particular AE is missing, this severity will be treated as missing in summaries and listed accordingly.

The following TEAE information will be summarized separately by contingency tables:

- Adverse events, regardless of relationship to study or co-administered prednisolone treatment, by primary SOC and PT
- Adverse events, suspected to be related to study treatment, by primary SOC and PT

- Adverse events, suspected to be related to co-administered prednisolone treatment, by primary SOC and PT
- Serious AEs, regardless of relationship to study or co-administered prednisolone treatment, by primary SOC and PT
- Serious AEs, suspected to be related to study treatment, by primary SOC and PT
- Serious AEs, suspected to be related to co-administered prednisolone treatment, by primary SOC and PT
- Adverse events, regardless of relationship to study or co-administered prednisolone treatment, by primary SOC, PT and maximum severity (mild, moderate, severe)
- Adverse events leading to study treatment discontinuation, regardless of relationship to study or co-administered prednisolone treatment, by primary SOC and PT
- Adverse events leading to study treatment discontinuation, suspected to be related to study treatment, by primary SOC and PT

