4 Change to protocol specified analyses

The baseline prednisolone dose subgroup categories have been updated from > 40 mg/day and ≤ 40 mg/day to ≥ 40 mg/day and < 40 mg/day to align with the planned prednisolone taper regimen.

Sustained remission at a timepoint refers to patients being without flare until that timepoint and in adherence to the protocol prednisolone taper regimen. As adherence to the protocol prednisolone taper regimen is a component of the sustained remission definition already; any redundant mention of adherence to prednisolone taper regimen has been removed throughout this document.

Any reference to the time point after clinical remission has been updated to be after Baseline; this aligns more clearly with what was planned to be analyzed.

5 Appendix

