5.1.2.2 Adverse event start date

Adverse events with completely missing onset dates will be considered to be treatment emergent. AEs with partially missing onset dates will also be included as treatment emergent when the month (if it exists) and the year occur on or later than the month and year of first administration of study treatment within this study.

Partial AE start dates are imputed with reference to the first administration of study treatment within this study as outlined in the table below.

The date value is split into day, month, year sections and referenced in the imputation table as outlined below.

	Day	Month	Year	
Partial AE Start Date	Not used	MON	YYYY	
Treatment Start Date	Not used	TRTM	TRTY	

The following matrix explains the logic behind the imputation.

Comparison of month section	MON missing	MON <trtm< th="">MON=TRTM	MON>TRTM	</trtm<>	MON=TRTM	MON>TRTM
YYYY missing	NC	NC	NC	NC
YYYY <trtm< td="">(D) =	(C) =	(C) =	(C) =	</trtm<>	(D) =	(C) =	(C) =	(C) =
	01JULYYYY	15MONYYYY	15MONYYYY	15MONYYYY
	Before Treatment Start	Before Treatment Start	Before Treatment Start	Before Treatment Start
YYYY=TRTY	(B) =	(C) =	(A)	(A)
	TRTSTD+1	15MONYYYY	= TRTSTD+1	= 01MONYYYY
	Uncertain	Before Treatment Start	Uncertain	After Treatment Start
YYYY>TRTY	(E) =	(A)	(A)	(A)
	01JANYYYY	= 01MONYYYY	= 01MONYYYY	= 01MONYYYY
	After Treatment Start	After Treatment Start	After Treatment Start	After Treatment Start

The following table is the legend to the logic matrix.

Relationship	
Before Treatment start	Partial date indicates AE start date prior to Treatment Start Date in this study
After Treatment start	Partial date indicates AE start date after Treatment Start Date in this study
Uncertain	Partial date insufficient to determine relationship of AE start date to Treatment Start Date in this study
Imputation calculation	
NC/Blank Uncertain	No convention
(A) After Treatment Start or Uncertain	MAX(01MONYYYY, TRTSTD+1)
(A) After Treatment Start or Uncertain	MAX(01MONYYYY, Treatment Start +1)
(C) Before Treatment Start	15MONYYYY

Relationship	
Before Treatment start	Partial date indicates AE start date prior to Treatment Start Date in this study
(D) Before Treatment Start	01JULYYYY
(E) After Treatment Start	01JANYYYY

Before imputing the AE start date, find the AE start reference date.

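### The SAP shortens the treatment-emergent AE limit from 20 weeks to 84 days after the last dose without declaring it, leaves open whether the limit covers new-onset events, and gives two ends to the safety observation period for early stoppers

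*SAP*

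**What the plan says.** Protocol 9.5.2 counts as treatment emergent an AE that starts after the first dose, or a pre-existing one that shows an "increase in severity after dosing based on preferred term and within last dose + 20 weeks". The same section restricts AE tables to events "with a start date during the on-treatment period".

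SAP 2.8.1 has almost the same sentence, but it ends with events that "increased in severity after dosing based on preferred term and within last dose + 84 days". It also says that AEs "will be presented for the whole study period", and that "Only treatment emergent AEs (TEAEs) will be summarized". The AESI summaries are a subsection of 2.8.1.

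SAP Section 4 lists three changes to protocol analyses. It opens with "The baseline prednisolone dose subgroup categories have been updated from" one pair of cut-offs to another, then covers redundant adherence wording and the move from clinical remission to Baseline as time origin. The AE limit is not there.

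On collection, Protocol 7.1.1 says "Adverse event monitoring should be continued for at least 20 weeks" after the last dose, and 7.1.3 requires SAE reporting for 20 weeks after stopping. Protocol 5.6.1, in a sentence about malignancies, says that nothing further is required after the two follow-up visits.

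SAP 2.1.1.4 defines the safety observation period twice. Its third bullet ends it at the last visit for patients who stopped study treatment early. Its formula ends it 84 days after the last administration for everyone. SAP 2.8.3 and 2.8.4.1 use this period to select on-treatment laboratory and vital-sign data.

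**The concern.** Safety and tolerability is a stated objective (Protocol Table 2-1), and Protocol 1.1 says that no trial data on this drug in giant cell arteritis had been reported. The window that decides which AEs reach the tables should therefore match the protocol, or the departure should be visible.

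There are two problems with the AE window. The limit moved by 56 days without an entry in Section 4, although a subgroup boundary was thought worth declaring there. And the limit is attached grammatically only to the worsening clause, so two programmers could build the treatment-emergent flag differently and produce different AE, SAE and AESI tables from the same data.

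Patients who stop injections early are encouraged to remain for all assessments (Protocol 5.6.2), and AEs are sought at every visit (7.1.1). Their later events will be collected. The question is whether they are summarized.

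The conflict in 2.1.1.4 is a separate drafting fault. It affects laboratory and vital-sign summaries, not the AE flag, and it stands whichever AE reading is adopted.

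**Working it through.** **1. The two limits.** Protocol: 20 × 7 = 140 days. SAP: 84 days = 12 weeks. Difference: 140 − 84 = 56 days (days 85-140 after the last dose).

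**2. Where 84 days comes from.** The target day of Week w is 7w + 1 (SAP Table 2-1). Week 48 is Day 337, Week 60 is Day 421, and 421 − 337 = 84. The limit equals the interval from the planned last dose to the last follow-up visit (Protocol 3.1). It also matches the 2.1.1.4 formula and the exposure definition in SAP 2.4.1.

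**3. Does the limit cover onset?**
- For: Protocol 9.5.2 requires the start date to fall in the on-treatment period.
- Against: in SAP 2.8.1 the limit follows only the worsening clause, and AEs are presented for the whole study.
- Weak evidence against: SAP 5.1.2.2 says "Adverse events with completely missing onset dates will be considered to be treatment emergent", with no upper bound. A missing date cannot be tested against a bound, so this settles little.

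The documents do not resolve the question.

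**4. In-study days between the limits, if onset is covered.** Days = max(0, min(days from last dose to end of follow-up, 140) − 84). End of follow-up is Day 421 (Week 60 target) or Day 435 (end of the Week 60 window).

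| Last dose | Day | +84 | +140 | Days lost to Day 421 | Days lost to Day 435 |
|---|---|---|---|---|---|
| Week 12 | 85 | 169 | 225 | 56 | 56 |
| Week 40 | 281 | 365 | 421 | 56 | 56 |
| Week 44 | 309 | 393 | 449 | 28 | 42 |
| Week 48 | 337 | 421 | 477 | 0 | 14 |

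At Week 40 the lost stretch contains the Week 56 and Week 60 visits. At Week 44 it contains Week 60 only.

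As a share of the patient's whole protocol window, the loss is 8/(w + 20): 8/24 = 33% for a last dose at Week 4, 8/32 = 25% at Week 12, and 8/60 = 13% at Week 40.

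**5. Scale.** The documents give no early-stop rate. As an assumption only, if 5-30% of the 50 patients stop by Week 40 and stay (2.5-15 patients), the removed follow-up is 2.5 × 56/365.25 = 0.4 to 15 × 56/365.25 = 2.3 patient-years. With about 25 per arm, one patient is 1/25 = 4 percentage points. A patient counts once per preferred term, so a late event changes a row only if that patient has no earlier event of that term.

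**6. Against the literal reading.** If new-onset events carry no limit, a patient with last dose on Day 85 contributes new events to Day 421. A 140-day onset limit would stop at Day 225, dropping 421 − 225 = 196 days. An 84-day limit would stop at Day 169, dropping 421 − 169 = 252 days.

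**7. SAP 2.1.1.4, last dose at Week 12 and followed to Week 60.** Formula: (85 − 1) + 85 = 169 days, ending on Day 169. Third bullet: Day 421. Difference: 252 days. Protocol Table 6-1 has six post-baseline laboratory visits (Weeks 4, 12, 28, 36, 44, 52). The last four fall after Day 169, so 4 of 6 are in or out depending on the definition. For completers the two versions differ by at most 435 − 421 = 14 days.

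**The case against.** The strongest reply is that 84 days is a coherent choice. It matches the last follow-up visit, the exposure definition and the 2.1.1.4 formula. It gives early stoppers and completers the same 12 weeks of visit-based ascertainment. With crude incidence, 140 days would give early stoppers up to 20 weeks against 12 for completers, which could tilt the comparison if stopping differs by arm. The SAP also draws on a program-level safety master analysis plan that is not available here and may hold the reason. This stands: the documents do not show that 140 days must be the main window. It does not excuse the missing declaration.

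Second, the ambiguity is inherited from Protocol 9.5.2 and was not created by the 84 days. True, but the SAP is where it must be settled, and its whole-study phrase adds to the doubt.

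Third, the effect needs a chain of conditions: the limit covers onset, the patient stops early and stays, a new event starts on days 85-140, and no earlier event shares its preferred term. Later events remain in the listings (SAP 2.1), and the death summary (SAP 2.8.2) states no 84-day limit. This also stands, and it limits the weight of the point.

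Fourth, simply declaring that the limit covers onset could itself remove late new events that the literal SAP text keeps (step 6). That is right, and the fix has to guard against it.

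**Conclusion.** The undeclared change from 140 to 84 days is certain, as is the contradiction in SAP 2.1.1.4. Both should be corrected. The consequence for the AE tables is conditional. If the limit covers onset, it removes 56 in-study days for each patient with a last dose at Week 40 or earlier who stays to Week 60, and 28-42 days for a last dose at Week 44. The number of such patients cannot be derived.

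A reader might infer more than the documents support:
- That the SAP definitely drops all new events on days 85-140. The wording leaves this open.
- That safety data are lost. The events stay in the listings; what is at risk is their place in the summaries.
- That completers lose eight weeks of events. Inside scheduled follow-up they lose 0-14 days. Whether AEs are collected from Week 60 to Day 477 is unsettled, because Protocol 5.6.1 conflicts with 7.1.1 and 7.1.3, and those passages must be reconciled.
- That the rule for completely missing onset dates is faulty. It is conservative and workable as it stands.

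The laboratory figure of 4 of 6 visits belongs to the 2.1.1.4 fault alone and adds nothing to the AE argument.

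**What to change.** 1. In SAP 2.8.1, state whether the limit covers onset as well as worsening, and bring the whole-study phrase into line with it.
2. Either restore the protocol's 20 weeks, or declare and justify 84 days in Section 4. In both cases show the AE, SAE and AESI summaries under both limits. If the limit is applied to onset, also summarize or list separately the new-onset events beyond it, so that no collected event drops out of view.
3. In SAP 2.1.1.4, keep one definition of the safety observation period.
4. In SAP 5.1.2.2, leave the rule for completely missing onset dates unchanged and apply any upper limit to partial dates only.

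The cost is one clarified sentence, one flag limit, one extra set of tables, one definition and, if 84 days is kept, one Section 4 entry. The downside is that a 140-day window counts more off-drug time and follows early stoppers by visit for longer than completers. For that reason neither window should be shown alone.

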2.8.1.1 Adverse events of special interest / grouping of AEs

Specific groupings of AEs of special interest (AESI) will be considered and the number of patients with at least one event in each grouping will be reported. Such groups consist of AEs for which there is a specific clinical interest in connection with secukinumab or AEs which are similar in nature (although not identical). Note that certain AEs may be reported within multiple groupings. These AESIs are updated on a regular basis at the secukinumab program level. The most recent version of the AESI search criteria form as described in the electronic Case Retrieval Sheet (eCRS) will be used for the reporting activity.

AESIs will be summarized regardless of study drug relationship, for each treatment group by grouping and PT.

2.8.2 Deaths

The number and percentage of deaths resulting from SAEs suspected to be related to study treatment and SAEs irrespective of study treatment relationship will be provided for each treatment group by primary SOC and PT.

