At every visit, each patient's disease activity and condition will be assessed in order to determine whether the patient can adhere to the defined prednisolone taper regimen (open-label fashion). If they cannot adhere to the taper regimen or are experiencing a flare (definition above), they must enter the "escape" arm and receive prednisolone at a dose determined by the physician based on clinical need and will continue to receive secukinumab 300 mg or placebo s.c. (still blinded).

Safety evaluation will be included in all visits including two safety follow-up visits performed 8 and 12 weeks after the last study drug administration at Week 48 (this will be at Week 56 and Week 60 for patients completing the study according to the protocol).

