### 5.6.2 Discontinuation of study treatment

Discontinuation of study treatment for a patient occurs when study treatment is stopped earlier than the protocol planned duration. Discontinuation of study treatment can be decided by either the patient or the investigator.

Study treatment must be discontinued under the following circumstances:

- Patient decision - patients may choose to discontinue study treatment for any reason at any time.
- The investigator believes that continuation would negatively impact the safety of the patient or the risk/benefit ratio of trial participation.
- Emergence of the following AEs:
  - Any severe AE or SAE that is not compatible with administration of study medication, including AEs that require treatment with an unacceptable co-medication
  - Life-threatening infection

- Onset of lymphoproliferative disease or any malignancy except for treated basal cell carcinoma, treated actinic keratosis, treated in situ carcinoma of the cervix, or non-invasive malignant colon polyps which are being or have been removed
- Any protocol deviation that results in a significant risk to the patient's safety.
- Pregnancy (see [Section 6.4.7](#) and [Section 7.1.4](#))
- Use of prohibited treatment as per recommendations in [Section 5.5.8](#).
- AEs, abnormal laboratory values or abnormal test results that indicate a safety risk to the patient.
- Any laboratory abnormalities that in the judgment of the investigator, taking into consideration the patient's overall status, prevents the patient from continuing participation in the study.

If discontinuation of study treatment occurs, the investigator must determine the primary reason for the patient's premature discontinuation of study treatment and record this information on the Dosage Administration CRF.

If study treatment discontinuation occurs because of study treatment unblinding, please refer to [Section 5.5.9](#).

Discontinuation of study treatment does not require the patient to be discontinued from the study and all ongoing visit assessments except in case of withdrawal of informed consent (see [Section 5.6.3](#)). Refer to [Section 6](#) for the visit schedule and assessments.

Patients who prematurely discontinue the study treatment (s.c. secukinumab or placebo) are encouraged to remain in the study to continue the study-related assessments until completion of the study.

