2.1.1.5 Study day

The study day for a baseline or post-baseline scheduled or unscheduled visit is defined as:

• Study day = (Date of visit) - (Baseline date) + 1

For visits prior to baseline, the study day is defined as:

• Study day = (Date of visit) - (Baseline date)

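### The SAP omits, without declaring it, the protocol's summary of on-treatment and post-treatment deaths, and gives no period for its own death table

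*SAP*

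**What the plan says.** Protocol 9.5.2 confines safety tables and figures to the on-treatment period. It then makes an exception for deaths: "a separate summary for death including on treatment and post treatment deaths will be provided". No time limit is attached to that exception. For adverse events, the same section sets the treatment-emergent limit at "within last dose + 20 weeks".

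SAP 2.8.2 is a single sentence. It plans, by treatment group, primary system organ class and preferred term, "The number and percentage of deaths resulting from SAEs suspected to be related to study treatment and SAEs irrespective of study treatment relationship". It has no on-treatment/post-treatment split and no period.

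SAP 2.8.1, the section before it, says: "Only treatment emergent AEs (TEAEs) will be summarized". Its definition of treatment-emergent covers events that start after the first dose, or that were present before and "increased in severity after dosing based on preferred term and within last dose + 84 days".

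SAP Section 4 records changes to the protocol's analyses. It lists the prednisolone subgroup cut-point, the removal of redundant adherence wording and the time origin for flare. It records nothing on deaths or on the move from 20 weeks to 84 days.

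On follow-up, Protocol 5.6.2 says that patients who stop the injections early "are encouraged to remain in the study to continue the study-related assessments until completion of the study". Protocol 3.1 provides for "two safety follow-up visits performed 8 and 12 weeks after the last study drug administration at Week 48", that is, at Weeks 56 and 60.

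**The concern.** The protocol treats death as the one outcome that should not be cut off at the end of the on-treatment period, and the SAP does not carry that through. A programmer working from the SAP has a table of fatal SAEs by organ class and term, with no stated period, directly after a rule that only treatment-emergent events are summarised. The likely result is a table cut at last dose + 84 days.

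The patients affected are those who stop injections early and stay in follow-up, as the protocol encourages. A death from an event that starts after their 84 days belongs in the protocol's death summary but need not appear in any safety summary that the SAP plans. Arms of about 25 patients aged 50 or over are small enough for a single death to change how a mortality comparison reads, and SAP Section 1 says that the results are meant to support a phase III programme.

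**Working it through.** **Inputs.** The convention is "Study day = (Date of visit) - (Baseline date) + 1" (SAP 2.1.1.5), so the target day for Week w is 7w + 1. SAP Table 2-1 agrees: Week 48 is Day 337 and Week 60 is Day 421. The treatment-emergent limit is last dose + 84 days in SAP 2.8.1 and last dose + 20 weeks (140 days) in Protocol 9.5.2. The last scheduled visit is Week 60.

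**Completers.** Last dose at Week 48: 337 + 84 = 421. The SAP limit ends on the Week 60 target day, so nothing is uncovered at target days. A Week 60 visit held late, up to Day 435 in Table 2-1, would leave at most 435 - 421 = 14 days.

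**Early stoppers.** Uncovered follow-up = 421 - (last-dose day + limit), or zero if negative.

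| Last dose | Day | Uncovered, 84-day limit | Uncovered, 20-week limit |
|---|---|---|---|
| Week 4 | 29 | 421 - 113 = 308 days (44 weeks) | 421 - 169 = 252 days (36 weeks) |
| Week 12 | 85 | 421 - 169 = 252 days (36 weeks) | 421 - 225 = 196 days (28 weeks) |
| Week 24 | 169 | 421 - 253 = 168 days (24 weeks) | 421 - 309 = 112 days (16 weeks) |
| Week 44 | 309 | 421 - 393 = 28 days (4 weeks) | 0 |
| Week 48 | 337 | 0 | 0 |

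The last column shows that restoring the protocol's 20-week limit for adverse events would not settle the point. Only a death summary without a limit brings the uncovered time to zero for every stopping time.

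**Size.** The documents give neither a stopping rate nor a mortality rate, so both are assumed here.

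- There are 15 possible early last-dose visits (Weeks 0, 1, 2, 3, 4, 8, ..., 44). Weighted equally, the mean last dose is 270/15 = Week 18, and the mean gap is 48 - 18 = 30 weeks.
- Assume that 10% to 30% of 50 patients stop early and stay to Week 60. That is 5 to 15 patients.
- Patient-years outside the limit: 5 × 30/52.18 = 2.9, up to 15 × 30/52.18 = 8.6.
- Assume 2% to 5% mortality per year. Expected deaths over both arms: 2.9 × 0.02 = 0.06, up to 8.6 × 0.05 = 0.43.
- Equal weighting places a third of the stops (5 of 15) at a last dose in Weeks 0 to 4. If stopping is instead uniform over calendar time to Week 48, the mean last dose is Week 22.1 and the mean gap is 48 - 22.1 = 25.9 weeks. The range becomes 5 × 25.9/52.18 × 0.02 = 0.05 to 15 × 25.9/52.18 × 0.05 = 0.37.
- One death in an arm of 25 is 1/25 = 4%.

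**The case against.** The strongest reply is that the exclusion is inferred. SAP 2.8.2 stands beside 2.8.1, not under it, and sets no limit. Where the SAP wants one nearby, for laboratory data in 2.8.3 and vital signs in 2.8.4.1, it opens with an explicit on-treatment restriction. Taken literally, 2.8.2 could tabulate every death from an SAE whenever it occurred. SAP 2.1.1.4 is also mixed on early stoppers: one bullet ends their safety observation period at the last visit, while the formula below it uses 84 days. This stands in part. A reader might infer that the SAP expressly excludes post-treatment deaths, and it does not. But the literal reading still lacks the post-treatment component that the protocol names, and the text leaves the programmer to choose.

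Three other stronger readings also go too far.

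- A reader might infer that any death more than 84 days after the last dose is lost. The limit applies to the onset or worsening of the event, not to the date of death. A death on day 150 from an SAE that began on day 60 is counted even under the restrictive reading.
- A reader might infer that such deaths vanish from all output. SAP 2.1 lists all data unless otherwise stated, and the study disposition table in 2.3.1 might show death as a reason for leaving, although it does not name that category.
- A reader might infer that keying the table to SAEs itself loses deaths. A fatal adverse event is an SAE under Protocol 7.1.2, and Protocol 7.1.1 continues monitoring to the end-of-study visit where that is longer than 20 weeks. Protocol 7.1.3 does narrow reporting to the sponsor's safety group after 20 weeks to events suspected to be related. That is a reason to count deaths directly, but it does not show that deaths would go unrecorded.

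Nothing in the documents shows that early stopping will differ between arms.

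**Conclusion.** The point holds as an undeclared omission combined with an ambiguity. The omission is certain: the protocol requires a summary that includes post-treatment deaths, the SAP does not plan one in those terms, and SAP Section 4 is silent. The consequence is conditional. If the treatment-emergent rule is carried over to the death table, deaths from events starting more than 84 days after the last dose, in early stoppers still under follow-up, drop out of the planned safety summaries.

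The expected count of 0.06 to 0.43 deaths is an upper-end illustration. It rests on assumed stopping and mortality rates, on equal weighting of the stopping visits, on every such patient staying to Week 60, and on treating all uncovered time as if any death in it came from a late-onset event. The most likely number of omitted deaths is zero. No efficacy endpoint or GO criterion is affected. The change is still worth making, because mortality is the safety result that should least depend on a programmer's reading, and one death is about 4% of an arm.

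**What to change.** Add to SAP 2.8.2: *All deaths from first dose to last study contact will be summarised by treatment group (Safety Set), split into on-treatment and post-treatment, irrespective of the treatment-emergent limit.* Keep the table by system organ class and preferred term as a second display and state its period. State also which limit, 84 days or 20 weeks, separates on-treatment from post-treatment deaths. The total does not depend on that choice, but the split does.

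If the sponsor prefers not to present post-treatment deaths, SAP Section 4 should record the departure from Protocol 9.5.2 and justify it.

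The cost is one sentence and one small table. It should need no new data collection: safety is evaluated at every visit to Week 60, and the SAP's date-imputation rules already use the date of death.
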